3. ABSTRACT

- **Background**

Propofol is the preferred drug of choice for procedural moderate to deep sedation. This can be titrated by using pharmacokinetic (PK) and pharmacodynamic (PB) models programmed in infusion pumps for target controlled infusion (TCI). In 2021 Vellinga et al published a study on the validation of the Eleveld model in patients undergoing general anesthesia. (Vellinga et al. 386-394) So far, the Eleveld model has not been externally validated for the use of procedural sedation in adult patients.

- **Main research question**

The primary objective is to identify effect-site target concentrations of propofol for the Eleveld model that is associated with procedural sedation; a modified observer's assessment of alertness and sedation (MOAAS) score 5-1 and the associated depth- of- anesthesia monitor parameter levels in adult patients. The secondary outcome is the time to reach MOAAS 5 representing fully awake after having stopped propofol infusion using the Eleveld model.

- **Design (including population, confounders/outcomes)**

Prospective observational study of adult patients undergoing procedures under sedation by using the Eleveld model for propofol. Descriptive statistics in SPSS.

Expected results

To have identified effect site concentrations (CET) of propofol using the Eleveld model for different levels of procedural sedation.

4. BACKGROUND

- **Introduction and rationale**
 - Since the Dutch guideline on procedural sedation outside of the operating room in 2012¹ has been published, procedural sedation practices in Dutch hospitals has taken a huge flight. Propofol is the preferred drug of choice for moderate to deep sedation. This can be titrated by using pharmacokinetic (PK) and pharmacodynamic (PB) models programmed in infusion pumps for target controlled infusion (TCI). Several PKPD models for TCI propofol are available. While most TCI systems incorporate PK or PKPD models for specific patient groups such as adults, children or older patients, the Eleveld model has been developed for TCI of propofol for general anesthesia and sedation in a broad range of patients.² In 2021 Vellinga et al published a study on the validation of the Eleveld model in patients undergoing general anesthesia.³ So far, the Eleveld model has not been externally validated for the use of procedural sedation in adult patients. The aim of this study is to identify effect-site target concentrations of propofol for the Eleveld model that are associated with moderate to deep sedation levels, MOAAS 5-1 and the associated BIS levels in adult patients.⁴ The secondary outcomes are: time to introduction of the endoscope and the time to reach MOAAS 5 after having stopped TCI propofol. The use of vasopressors such as ephedrine, phenylephrine or norepinephrine. The need for airway maneuvers such as chin lift, jaw thrust or nasopharyngeal airway.

- **Research question**

Primary outcome

To identify CET propofol using the Eleveld model for different levels of procedural sedation as measured by MOAAS and EEG monitoring.

Secondary outcomes

- Relevant clinical endpoints i.e. time to introduction of the endoscope, the time to reach MOAAS 5 after having stopped TCI propofol.
- The use of vasopressors such as ephedrine, phenylephrine or norepinephrine.
- The need for airway maneuvers such as chin lift, jaw thrust or nasopharyngeal airway.

5. METHOD

5.1 Description study design

This is a prospective observational study. Adult patients undergoing sedation for endoscopic procedures in the UMCG between 01-01-2024 and 01-01-2025 will be included. Written informed consent will be obtained prior to the procedure. Exclusion criteria are: age <18 years, the use of esketamine during the procedure, the use of benzodiazepines prior or during the procedure, hearing disability and a BIS quality index < 50.

Monitoring

All patients will be monitored according to the departmental protocol⁵ (<https://umcg.zenya.work/portal/#/document/217c7341-ad32-4655-b2e7-6e49665e8869>) with a Philips IntelliVue MP30 monitor (Philips Medizin Systeme Boeblingen GmbH, Boeblingen). This consists of continuous 3-lead electrocardiogram (ECG), peripheral hemoglobin oxygen saturation (SpO₂), respiration rate, end-tidal carbon dioxide concentration (etCO₂) using a Medtronic Microstream™ Advance Adult Oral-Nasal CO₂ Filter Line, noninvasive blood pressure (NIBP) with a measurement interval of 5 minutes.

Dose-response relationship will be determined with a depth-of-anesthesia-monitor as per the department's standard protocol for sedation. Depth of sedation will be monitored using non-invasive monitoring (BIS® monitor (BIS Vista, Medtronic, Boulder, CO, USA and Masimo Root with Sedline® Masimo Irvine, CA). The Modified Observer's Assessment of Alertness and Sedation score (MOAS score) will be noted every 10 minutes and is used to record the depth of sedation. All data from the vital signs monitor and infusion pumps will be automatically stored in an electronic medical record system (Epic Systems corporation, [name]).

Sedation protocol

Sedation will be administered using Target-Controlled Infusions (TCI) of propofol (administered by effect-site TCI using the Eleveld model) and remifentanil (administered by effect site TCI using the Eleveld model). Target controlled infusion of propofol and remifentanil is according the departmental protocol (<https://umcg.zenya.work/portal/#/document/217c7341-ad32-4655-b2e7-6e49665e8869>). TCI propofol will be administered by stepwise increasing effect-site targets until the desired depth of sedation has been reached as per clinical practice.

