5.3 Population

5.3.1 Inclusion and exclusion criteria				

 Inclusion criteria: Adult patients for procedural sedation in the UMCG between 01-01-2024 and 01-01-2025. Exclusion criteria: age <18 years; use of esketamine during the procedure, use of benzodiazepines prior or during the procedure, hearing disability, BIS quality index < 50 				
5.3.2 Number of participants				

 Target total number of participants: 75 sample size based on previous literature Vellinga et al. Target number of UMCG participants: three groups of 25 patients; patients age \geq 18- <65, patients age \geq 65 and over, patients BMI \geq 30. 				
5.3.3 Study subjects (tick all that apply)				

 Healthy volunteers Patients 	
 
 no	
 
 yes	
 
	no	yes	
no				
yes				
<text>				
5.3.4 Subject classification (tick all that apply)				

 Participants \geq 16 years Children between 12 and 16 years (if applicable, written informed consent will be obtained from child and both parents - if both have authority, or guardian [or parents/guardian only if incapacitated child]) Children < 12 years (if applicable, written informed consent will be obtained from both parents - if both have authority, or guardian) 	
 
 yes	
 
 no	
 
 no	
 
	yes	no	no
yes				
no				
no				
<text>				
5.3.5 Incapacitated adults				
Participants are incapacitated/ decisionally incompetent adults (if applicable, written informed consent will be obtained from legal representative)	no			
<text>				

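### The only EEG signal-quality rule is a BIS-based patient exclusion: it leaves Sedline readings unscreened and discards MOAAS and concentration data that do not depend on the EEG

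*Protocol*

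**What the plan says.** Section 5.1 (Monitoring) lists the depth-of-sedation equipment as a BIS Vista "and Masimo Root with Sedline". The sentence before it speaks of one monitor: "Dose-response relationship will be determined with a depth-of-anesthesia-monitor as per the department's standard protocol for sedation". Neither sentence says whether each patient wears one device or both, or how a device is chosen.

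The EEG measure is described in three ways:

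- Abstract, primary objective: "the associated depth- of- anesthesia monitor parameter levels in adult patients" (no device named).
- Section 4, aim in the introduction: "MOAAS 5-1 and the associated BIS levels in adult patients" (BIS only).
- Section 4, listed primary outcome: effect-site concentrations "for different levels of procedural sedation as measured by MOAAS and EEG monitoring" (no device named).

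The one signal-quality rule is "BIS quality index < 50". It stands in the exclusion criteria of Section 5.3.1, next to age and hearing disability, and is repeated in the exclusion list of Section 5.1. No quality criterion is given for Sedline.

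MOAAS is scored by observation every 10 minutes. Infusion-pump data go automatically into the electronic record. The target is 75 patients in three groups of 25 (Section 5.3.2), and the analysis is descriptive only (Section 5.9).

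**The concern.** A signal-quality rule should remove measurements that cannot be trusted and leave the rest. This one acts on the patient, and it looks at one of the two devices. Two things follow.

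First, the primary outcome links effect-site concentration to sedation level by MOAAS and by EEG. A patient whose BIS signal is poor loses both parts, although only the EEG part is in doubt. The MOAAS part then describes patients selected on a property of an EEG sensor. Whether these differ from the others in concentration or depth of sedation is unknown, but the plan has no reason to take that risk.

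Second, a Sedline reading of any quality is accepted, because no stated rule touches it. With a purely descriptive analysis, the values tabulated per MOAAS level are themselves the result, so readings of unknown quality go straight into it.

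The uneven wording of the EEG measure adds to this. A reader cannot tell from the protocol whether the Sedline index belongs to the primary outcome or is recorded beside it.

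**Working it through.** The one figure involved reproduces: 3 groups x 25 = 75. No formula applies beyond that, because the point concerns what a stated rule does when it is followed. The check is to apply the rule under each reading of device use.

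| | Every patient wears both devices | Each patient wears one device |
|---|---|---|
| BIS levels available from | all patients kept, up to 75 | only patients with BIS, fewer than 75 |
| Can the exclusion be judged? | yes, for everyone | not for Sedline-only patients |
| Are Sedline readings screened? | no | no |
| Effect of poor BIS signal | patient removed, with MOAAS, concentrations and any usable Sedline values | patient removed, with MOAAS and concentrations |
| Does eligibility depend on the device worn? | no | yes: poor signal removes a BIS patient but not a Sedline patient |

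The third and fourth rows go the same way in both columns, so they do not depend on how the device sentence is read. The other three rows do.

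The fourth row requires that MOAAS and concentration data stand without the EEG:

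1. MOAAS is an observer's score, and Section 5.1 makes it the record of sedation depth. No EEG value enters it.
2. The effect-site concentration comes from the Eleveld model in the infusion pump. No biomaterials are collected (Section 5.6), so no measured concentration is involved.
3. A patient excluded for BIS quality therefore still has complete data for the concentration-by-MOAAS part of the primary outcome.

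On the wording of the measure: the Abstract objective and the listed primary outcome can hold either index or both. The Section 4 aim can hold BIS only. These fit together only if the Sedline index is outside the aim, and the protocol does not say so.

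**The case against.** Several points can fairly be made for the plan.

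*The devices are joined by a plain conjunction.* If all patients wear both, BIS exists for everyone, the exclusion can be judged for everyone, and selection does not depend on the device. This stands. A reader might infer that the EEG part of the primary outcome must either mix two indices or rest on an unplanned subset of patients. The documents do not support that: it holds only if each patient wears one device, which the text leaves open, and no pooling of the indices is planned anywhere.

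*The departmental sedation protocol may settle device use.* Section 5.1 refers to it, and it is not at hand. This stands as a reason not to assume an answer. A short statement in the study protocol is still needed, because the exclusion criterion depends on it.

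*The aim is not BIS-only throughout.* Correct. Only the Section 4 aim is, and the point is limited to that mismatch.

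*Tables by device belong in an analysis plan.* Also correct, and their absence from the protocol is not the criticism. But the exclusion criteria and the aim are protocol text, and a later plan cannot easily recover the data of a patient who has already been excluded.

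*One cohort with good EEG and MOAAS together is tidy.* It is, but that cohort can be shown as a subset without discarding the other patients.

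**Conclusion.** The point holds in a limited form. Under either reading of device use, the signal-quality rule works badly: Sedline readings are unscreened, and a poor BIS signal costs MOAAS and concentration data that do not depend on it. If some patients wear Sedline only, two further consequences follow: the exclusion cannot be judged for those patients, and BIS levels come from fewer than 75. If all wear both, these two do not arise.

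No size can be attached. The protocol gives no device split, no expected share of patients below the BIS threshold, and no difference or spread for either index. Any figure for lost precision or for a shift between the indices would be assumption alone.

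The MOAAS part of the primary outcome is touched only through the exclusion. This is a flaw in a rule and in wording, worth correcting because the correction is cheap. It does not put the study's design in doubt.

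**What to change.** 1. Take the BIS quality index out of the patient exclusion criteria in Sections 5.1 and 5.3.1.
2. Replace it with a signal-quality criterion applied to individual EEG readings, one for each device on that device's own quality measure. A reading that fails is dropped as an EEG value only; the patient's MOAAS scores and concentrations are kept.
3. State in Section 5.1 whether each patient wears one device or both and, if one, how it is chosen.
4. Align the Section 4 aim with the Abstract objective by naming the BIS index, the Sedline index, or both.
5. Report the two indices separately, with the number of patients behind each.

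The cost is a few sentences in the protocol, a quality criterion for Sedline that the sponsor has to set, and a second table. The downside is that the n behind each EEG index becomes smaller and varies between MOAAS levels, so it must be shown with each summary.

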5.9 Data analysis

- Justification of sample size (e.g. power analysis)
- Convenience sample size based on pre lit Vell
- Statistical analysis: Describe in detail the statistical analysis used to test the research question.
- Only descriptive statistics will be used

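### Sedation is given with propofol and remifentanil together, but the primary outcome is propofol CET per sedation level without naming the remifentanil level at which it was observed

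*Protocol*

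**What the plan says.** Section 5.1 (Sedation protocol) names two drugs, each given by effect-site TCI: propofol, and "remifentanil (administered by effect site TCI using the Eleveld model"). On targets it says only "Target controlled infusion of propofol and remifentanil is according the departmental protocol". That departmental protocol is cited by link and is not reproduced. The one titration rule written out concerns propofol, whose target is raised in steps until the wanted depth is reached. Section 5.1 also says that the depth-of-anesthesia monitor will be used to determine a dose-response relation.

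The result is defined on propofol only. The primary outcome in section 4 is "To identify CET propofol using the Eleveld model for different levels of procedural sedation as measured by MOAAS and EEG monitoring". The expected result in section 3 is "To have identified effect site concentrations (CET) of propofol using the Eleveld model for different levels of procedural sedation". Remifentanil is named nowhere outside the sedation paragraph of 5.1.

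Three other statements bear on the point:

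- Section 5.3.1 excludes "use of esketamine during the procedure, use of benzodiazepines prior or during the procedure". This leaves remifentanil as the only co-administered drug that the sedation protocol names.
- Section 5.3.2 sets "Target number of UMCG participants: three groups of 25 patients", defined by age and BMI.
- Section 5.9 states "Only descriptive statistics will be used". Section 5.1 says that "All data from the vital signs monitor and infusion pumps will be automatically stored in an electronic medical record system".

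**The concern.** When two drugs are infused together, the propofol concentration recorded at a sedation score describes one component of a pair. The table this plan would produce lists a propofol CET for each MOAAS/EEG level and leaves the other component out.

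Two things are at stake. The first is scope. A reader who knows from 5.1 that remifentanil was given, but not at what level, cannot judge whether the CETs apply to sedation with a different remifentanil level or with none. The second is comparability within the table. If deeper levels were reached with more remifentanil, or with less, the step in propofol CET from one level to the next is not the propofol step alone, and the dose-response relation that 5.1 aims for is mixed with the second drug. An informal comparison of the age and BMI groups would meet the same difficulty.

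**Working it through.** **The plan's own figure.** The only design number is the sample size: 3 groups × 25 = 75, which matches the stated total. Section 5.9 calls it a convenience sample, so there is no power or precision calculation to reproduce, and this point does not depend on one.

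**The sections side by side.**

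| Place in the protocol | Propofol named | Remifentanil named |
|---|---|---|
| 3, objective, design and expected results | yes | no |
| 4, aim and primary outcome | yes | no |
| 5.1, sedation protocol | yes | yes |
| 5.3, population | no | no |
| 5.9, data analysis | no | no |

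The drugs are described in one place and the result in others, and nothing links the two.

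**How large could the effect be?** The documents give neither the effect of remifentanil on the propofol CET needed for a given score nor its pattern of use. The reductions below are assumptions, starting at zero. Let r be the fraction by which remifentanil lowers the propofol CET at a given score.

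*Single value.* Reported CET ÷ CET without remifentanil = 1 − r.

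- r = 0: 1.0
- r = 0.1: 0.9
- r = 0.3: 0.7
- r = 0.5: 0.5

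*Ratio of CETs between two levels or groups.* Distortion = (1 − r1)/(1 − r2).

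- Equal r, including r = 0 in both: 1.00
- 0% against 10%: 0.9/1.0 = 0.90, or 1.0/0.9 = 1.11
- 10% against 30%: 0.7/0.9 = 0.78, or 0.9/0.7 = 1.29
- 10% against 50%: 0.5/0.9 = 0.56, or 0.9/0.5 = 1.80

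The direction depends on which level or group has the larger reduction.

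**Compared with sampling error.** Suppose each of 25 patients contributes one CET at a level. The 95% half-width of the mean is then 0.413 SD (the t quantile on 24 degrees of freedom divided by √25). For assumed coefficients of variation of 20%, 30% and 40%, that is about 8%, 12% and 17% of the mean. A shift of 20% or more would exceed all three, a shift of 10% would exceed only the first, and a shift of 0% exceeds none. Depending on facts not in the documents, the omitted drug could matter more than sampling error or not at all.

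**The case against.** The strongest reply is that the protocol does not claim what it is being faulted for. Sections 3 and 4 look for concentrations associated with sedation levels, in a study declared observational, and 5.1 names both drugs openly. A reader might infer that the plan attributes sedation to propofol alone. The text does not say so, and that reading should not be pressed. What stands is narrower: the outcome is silent on the second drug, while 5.1 uses dose-response language for the first.

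A reader might also infer that the results are confounded. The documents do not support that either. The departmental protocol may hold remifentanil at a common target. The CETs would then be comparable across levels at that target, although still specific to it. No comparison between the three groups is a stated objective or outcome: they are recruitment targets, and the analysis is descriptive. The group argument is a caution about interpretation, not an error in a planned contrast.

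It is fair, too, that the assumed reductions come from outside the documents, and that zero belongs in the range.

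Finally, tabulating a co-administered drug is often left to a statistical analysis plan, which may exist. Nothing in the protocol bars it: the pump data are stored, and a summary of remifentanil CET is still descriptive. This answers part of the point. It does not answer the wording of the primary outcome or the scope of the conclusion, both of which belong in the protocol.

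**Conclusion.** The point holds as one about how the primary result is defined. Sedation is reached with two infused drugs, and the result is stated for one of them without the level of the other. The reported CETs hold for the concurrent remifentanil level, which the outcome does not identify. Whether they carry over to another level, and whether CETs at different sedation levels form a propofol dose-response, cannot be judged unless that level is reported.

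The size of any effect cannot be derived from the documents. Under the assumed reductions of 0% to 50%, it runs from no distortion to a substantial one. Confounding is possible but not demonstrated. The point does not invalidate the study. It should be fixed because the meaning of the main table depends on it and the remedy is small.

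**What to change.** 1. In sections 3 and 4, word the objective, primary outcome and expected result as propofol CET per MOAAS/EEG level during combined propofol-remifentanil sedation.
2. In 5.9, state that the pump-predicted remifentanil CET at each MOAAS/EEG reading will be extracted from the stored pump data. Summarise it beside propofol CET for each level, and for each group if groups are reported.
3. Limit the conclusion to combined sedation. Describe differences in CET between levels or groups as differences in propofol only where the remifentanil summaries are similar.

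The cost is one more extracted variable and a narrower conclusion. The analysis stays descriptive, no patient is added, no cell becomes smaller and no dosing change is implied.

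Stratifying by remifentanil CET is not required, because cells would soon be thin. MOAAS is noted every 10 minutes. If procedures last 30 to 60 minutes (assumed), each patient gives 3 to 6 readings, so a group of 25 gives 75 to 150. Spread evenly over five levels, that is 15 to 30 readings per level; two strata would leave 7.5 to 15. Readings within a patient are correlated, and rarely used levels would have fewer.

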5.2 Design

5.2.1 Mono- or multicenter study	Mono-center study yes	Multicenter study
<text>		
5.2.2 Retrospective study (available data/biomaterials only) or prospective study (data/biomaterials from [some] participants will be collected in the future).	Retrospective study No skip Sections 5.4.2/5.5.6	Prospective study Yes skip Sections 5.4.1
<text>		
5.2.3 Cross-sectional or follow-up study	Cross-sectional study yes	Follow-up study
<text>		
5.2.4 Quantitative or qualitative study (click both if mixed-method)	Quantitative study yes	Qualitative study
<text>		
5.2.4 Pilot study		No
<text>		

5.3 Population

5.3.1 Inclusion and exclusion criteria				

 Inclusion criteria: Adult patients for procedural sedation in the UMCG between 01-01-2024 and 01-01-2025. Exclusion criteria: age <18 years; use of esketamine during the procedure, use of benzodiazepines prior or during the procedure, hearing disability, BIS quality index < 50 				
5.3.2 Number of participants				

 Target total number of participants: 75 sample size based on previous literature Vellinga et al. Target number of UMCG participants: three groups of 25 patients; patients age \geq 18- <65, patients age \geq 65 and over, patients BMI \geq 30. 				
5.3.3 Study subjects (tick all that apply)				

 Healthy volunteers Patients 	
 
 no	
 
 yes	
 
	no	yes	
no				
yes				
<text>				
5.3.4 Subject classification (tick all that apply)				

 Participants \geq 16 years Children between 12 and 16 years (if applicable, written informed consent will be obtained from child and both parents - if both have authority, or guardian [or parents/guardian only if incapacitated child]) Children < 12 years (if applicable, written informed consent will be obtained from both parents - if both have authority, or guardian) 	
 
 yes	
 
 no	
 
 no	
 
	yes	no	no
yes				
no				
no				
<text>				
5.3.5 Incapacitated adults				
Participants are incapacitated/ decisionally incompetent adults (if applicable, written informed consent will be obtained from legal representative)	no			
<text>				

